5.6. Prior and Concomitant Medications

5.6.1. Prior Medication

All non-cancer medications received by subjects within 30 days prior to Screening will be recorded as prior medications.

All anti-cancer medications that the subject received at any point, irrespective of the time relative to screening, will be recorded from the medical history.

5.7. Discontinuation

A subject may discontinue from study drug treatment, but may agree to receive long-term follow-up phone calls.

5.7.1. Study Drug Discontinuation

The following reasons are considered sufficient to discontinue a subject from study drug treatment:

AE

Death

PD or relapse which meets protocol-defined response criteria (Section 17.4)

Other (the reason should be discussed between the Investigator and Sponsor Medical

Allogeneic HCT

Pregnancy

Protocol deviation

Lost to follow-up

Other (the reason should be discussed between the Investigator and Sponsor Medical

Monitor, and should be recorded on the case report form [CRF])

All subjects discontinued from study treatment due to any reason other than withdrawal of consent for follow-up will undergo assessment at follow-up visits.

If the subject discontinues study treatment due to an AE, the Investigator will follow the subject until the AE has resolved or stabilized, or until the subject is available for follow-up.

Response criteria-met or clinical PD/relapse is considered a sufficient reason to discontinue study drug treatment; however, the Investigator may continue the subject on study drug treatment until the Investigator has determined alternative AML therapies and considers the study drug treatment to be no longer beneficial to the subject. The decision to discontinue a subject from study drug treatment remains the responsibility of the Investigator and should not be delayed or refused by the Sponsor.

When one of the study drugs is discontinued due to toxicities, Investigators may continue the other study drug if this is considered to be safe and in the best interest of the subject after consultation with the Sponsor Medical Monitor.

5.7.2. Study Discontinuation

If a subject is withdrawn from the study (eg, has completed the 30-day safety window and withdrawn consent for receiving long-term follow-up, or has proceeded to next treatment regimen), the Investigator will complete and report the observations as thoroughly as possible up to the date of withdrawal, including the date of last treatment and the reason for withdrawal.

All subjects who are withdrawn from the study should complete protocol-specified withdrawal procedures.

Subjects may be withdrawn from the study at any time after signing the Informed Consent Form (ICF) for the following reasons:

Withdrawal by subject

Death

PD or relapse

Lost to follow-up

Other (the reason should be specified on the CRF)

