2.4.3.1. Exploratory Efficacy Endpoints

The exploratory efficacy endpoints may include the following assessments:

Transplantation rate: Percent of subjects undergoing allogeneic HCT directly following protocol-specified treatment with no intervening AML therapy

Event-free survival (EFS): Time from first dose date until relapse after CR or CRi, refractory disease, or death from any cause, whichever is observed first

Overall survival (OS): Time from first dose date until death from any cause

Transfusion independence

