6.4.1. End-of-Treatment Bone Marrow Re-biopsy/Aspirate (Part 1 and Part 2)

To search for possible mechanisms of acquired resistance to milademetan and quizartinib combination, a bone marrow re-biopsy or aspirate will be performed in subjects who have achieved an initial CR, CRi, MLFS, or PR but later relapse (after CR or CRi) or develop PD (after MLFS or PR) while on therapy. Bone marrow re-biopsy or aspirate would be performed within 30 days following the last dose of study drugs, prior to initiating subsequent AML therapy.

6.5. Follow-up Phase – Part 1 and Part 2

All subjects who discontinued study treatment will enter the Follow-up Phase and will undergo the following assessments. Subjects discontinued from study treatment because of withdrawal of consent for follow-up are exempted.

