6.5.2. Long-term Survival Follow-up

The Long-term Survival Follow-ups should occur every 3 months (\pm 2 weeks) after the first 30-day Follow-up visit until subject death or until the Sponsor terminates the study. Additionally, the most updated survival follow-up status may be collected when the Sponsor performs survival analysis (for example, asking for survival status again when a subject had survival follow-up 2 months prior).

The following information will be collected, if feasible:

- Subject survival status.

- Date and cause of death, if applicable.

- Subsequent AML therapy.

- HCT and HCT-relevant information, if performed.

If direct contacts are not possible or if Long-term Survival Follow-up is not performed due to withdrawal of consent, subject refusal to participate in long-term follow-up, or loss to follow-up, the site must make every effort to collect survival status from public records (eg, death certificates) in accordance with local laws and document as best possible the specific reason for inability to collect long-term follow-up data.

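### Section 5.7.2 allows withdrawal from the study at PD, relapse or next therapy, contradicting the survival follow-up in Sections 5.7.1, 6.5 and 6.5.2; if applied, it would informatively censor exploratory OS.

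*Combined protocol and SAP*

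**What the plan says.** Section 5.7.2 concerns leaving the study, as distinct from stopping study drug, which is covered in 5.7.1. Its opening sentence illustrates a withdrawn subject as one who has completed the 30-day safety window and "withdrawn consent for receiving long-term follow-up, or has proceeded to next treatment regimen". For such a subject "the Investigator will complete and report the observations as thoroughly as possible up to the date of withdrawal". The section then states: "Subjects may be withdrawn from the study at any time after signing the Informed Consent Form (ICF) for the following reasons". The list that follows includes PD or relapse.

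The other sections point the opposite way:

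- Section 5.7.1: "All subjects discontinued from study treatment due to any reason other than withdrawal of consent for follow-up will undergo assessment at follow-up visits".
- Section 6.5: "All subjects who discontinued study treatment will enter the Follow-up Phase". Its only exception is: "Subjects discontinued from study treatment because of withdrawal of consent for follow-up are exempted".
- Section 6.5.2: contact every 3 months "until subject death or until the Sponsor terminates the study", collecting survival status, date and cause of death, subsequent AML therapy and HCT. Footnote c of each Schedule of Events table repeats this follow-up rule.

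The endpoint that depends most on this follow-up is defined in Section 2.4.3.1: "Overall survival (OS): Time from first dose date until death from any cause". It is one of the exploratory endpoints that may be assessed. Section 11.4 plans a Kaplan-Meier summary for DOR only. The documents give no OS analysis and no OS censoring rule.

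**The concern.** A site that withdraws a subject from the study at PD, relapse or the start of another regimen has followed 5.7.2. A site that keeps the same subject in survival follow-up has followed 5.7.1, 6.5 and 6.5.2. With about 15 sites in Part 1 and about 15 more possible in Part 2, practice can differ between sites without anyone deviating from the protocol.

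Subjects who have progressed or relapsed can be expected to face a higher risk of death than those who have not. Ending their observation at that point breaks the independence of censoring and death on which Kaplan-Meier rests, and the survival curve is pushed up.

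DOR has a narrower exposure. Relapse is already a DOR event, so withdrawal at relapse costs it nothing. Death is also a DOR event, however. A responder who moves to another regimen while still in remission, and is withdrawn for that reason, could die unobserved.

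Survival data not collected at the time may not be recoverable later.

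**Working it through.** The plan states no OS assumption, event count or dropout rate, so there is no figure of its own to reproduce. The check has three steps.

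**1. The texts side by side**

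| Event | Section 5.7.2 | Sections 5.7.1, 6.5, 6.5.2 |
|---|---|---|
| PD or relapse | Permitted reason to leave the study | Subject enters follow-up |
| Next AML regimen | Example of a withdrawn subject | Recorded during follow-up, which continues |
| Consent for follow-up withdrawn | Example of a withdrawn subject | Exempt from follow-up |
| Data after the event | Reported up to the withdrawal date | Every 3 months to death or Sponsor termination |

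Only the consent row agrees. Section 6.5.2 also requires a public-records search when direct contact is not possible, or after consent withdrawal, refusal or loss to follow-up. It does not name PD or a next regimen.

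**2. Direction**

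Let the time to first event be exponential with weekly rate L. A share s of first events is PD or relapse, and the rest are deaths. Survival after PD is exponential with rate μ = ln 2 / m, where m is its median. Then

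S(t) = exp(−Lt) + [sL/(L−μ)]·[exp(−μt) − exp(−Lt)].

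L is chosen so that S(20.9) = 0.5, where 20.9 weeks is the single-agent 30 mg median in Section 1.1. The death hazard is (1−s)L before PD and μ after it.

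- s = 0.85, m = 8: μ = 0.0866 and L ≈ 0.064. The hazard before PD is 0.15 × 0.064 ≈ 0.0096, so the ratio is about 9.
- s = 0.5, m = 14: μ = 0.0495 and L ≈ 0.057. The hazard before PD is 0.5 × 0.057 ≈ 0.028, so the ratio is about 1.7.

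Censoring subjects at or soon after PD removes them when their hazard is higher, so the estimate moves up.

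**3. Size**

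Input from the documents: true medians of 20.9 and 27.3 weeks (Section 1.1), used only as anchors. Assumptions not in the documents: s from 0.5 to 0.85, m from 8 to 14 weeks, and the share of subjects with PD who are withdrawn. Withdrawn subjects are censored at PD plus 30 days (30/7 = 4.3 weeks), because Section 6.5.1 collects survival status 30 (±5) days after the last dose. Each scenario simulates 200,000 subjects. The entries are Kaplan-Meier medians in weeks for a true median of 20.9.

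| s | m | 25% withdrawn | 50% | 100% |
|---|---|---|---|---|
| 0.50 | 8 | 21.5 | 22.3 | 24.4 |
| 0.50 | 14 | 21.2 | 21.6 | 22.6 |
| 0.70 | 8 | 21.8 | 22.9 | 27.2 |
| 0.70 | 14 | 21.3 | 22.0 | 24.5 |
| 0.85 | 8 | 22.0 | 23.5 | 30.4 |
| 0.85 | 14 | 21.4 | 22.3 | 27.2 |

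For a true median of 27.3 weeks the ranges are 28.0 to 29.1 (25%), 29.0 to 31.7 (50%) and 31.7 to 44.9 (100%).

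A second model tests sensitivity. OS is exponential, 60% have PD first, and PD falls at a Beta-distributed fraction of survival (mean 0.3 or 0.5, a+b from 2 to 10). The 30-day lag is the same. For a true 20.9 weeks it gives about 23 to 24.5 (half withdrawn) and 27 to 32 (all). For 27.3 it gives about 30 to 33 and 36 to 44.

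**The case against.** The strongest reply is that 5.7.2 only says subjects may be withdrawn. The mandatory wording in 5.7.1 and 6.5, repeated in the Schedule of Events footnotes, requires follow-up. OS is optional and exploratory in a single-arm Phase 1 study, no OS analysis is specified, and no comparison with the medians in Section 1.1 is planned. Section 6.5.1 captures survival status and subsequent therapy at 30 days, and 6.5.2 has a public-records backstop.

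Most of this stands, and it limits what can be claimed. A reader might infer that survival data are lost and OS is overstated as a matter of course. The documents do not support that, because loss occurs only where sites use the permission. A reader might also censor at the date of PD, which under the second model gives 31 to 37 weeks for a true 20.9 with everyone withdrawn. That ignores the 30-day contact, and Section 5.7.1 lets treatment continue past PD.

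The reply does not remove the conflict. Permissive wording is what allows sites to differ, and the backstop does not name the two situations at issue. It is also unclear whether the 30-day window in the 5.7.2 example applies to its next-regimen clause.

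**Conclusion.** The contradiction is in the current text and should be reconciled. If 5.7.2 is applied, exploratory OS would be informatively censored and probably overstated, and some deaths in remission could be missed for DOR.

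The size cannot be derived from the documents. On the stated assumptions, a true 20.9-week median reads about 0.7 to 2.6 weeks high if half of subjects with PD are withdrawn (21.6 − 20.9; 23.5 − 20.9). If all are withdrawn it reads 1.7 to 9.5 weeks high (22.6 − 20.9; 30.4 − 20.9), or about 11 under the second model (32 − 20.9). The full-withdrawal figures require every site to set aside 5.7.1 and 6.5, so they are an upper bound within these models and not a forecast.

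Response rates, including the two-cycle response used for the Part 2 futility rule, do not use survival status after PD and are unaffected. A reader might infer that the main efficacy conclusions are at risk; they are not. The matter is worth correcting because it decides which data are collected and the remedy is nearly free.

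**What to change.** In Section 5.7.2:

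- Remove PD or relapse from the reasons for withdrawal from the study.
- Remove the clause on having moved to the next regimen from the example in the opening sentence.
- Add a sentence that PD, relapse and the start of subsequent AML therapy do not end survival follow-up under Section 6.5.2.

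Align the study-discontinuation reasons on the CRF with the shortened list. The CRF is not part of the documents, so its present wording needs checking. Leave the treatment-discontinuation reasons in 5.7.1 unchanged, since this concerns follow-up only. If OS is to be reported, the SAP should also say that subjects not known to have died are censored at the date last known alive.

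The cost is the wording of one section and one CRF reason list. The 3-monthly contacts are already planned, so no visits or procedures are added.

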5.7.3. Subject Replacement

For a subject to be considered evaluable for DLT, the subject must have received at least 75% of the prescribed Cycle 1 doses and completed safety assessments of the DLT evaluation period or experienced a DLT in this period. Subjects who are unable to complete at least 75% of prescribed Cycle 1 doses of milademetan and quizartinib or unable to be evaluated for safety during the DLT evaluation period as a result of unequivocal progression of disease or non-compliance may be replaced.

In both Part 1 and Part 2, subjects with a known record of FLT3-ITD mutant AML within the last 30 days from informed consent based on local testing can enroll in the study. However, FLT3-ITD status will be tested in a central laboratory for confirmation of eligibility and any results indicating absence of FLT3-ITD will be communicated to the Investigator for possible discontinuation of the subject from study participation if ongoing clinical benefit is not observed. Subjects in Part 2 who do not show confirmation of FLT3-ITD mutation by central laboratory testing will be replaced. However, those who are deriving clinical benefit may be allowed to continue treatment.

5.7.4. Subject Re-screening Procedures

Re-screening is permitted for any subject who failed to meet eligibility criteria upon initial screening. The subject identification number must remain the same at the time of re-screening. The initial screening information and the reason why the subject is ineligible for the initial evaluation will be recorded on the Screening Log. If the subject successfully repeats the failed initial screening assessment(s) within the 14-day Screening period, the subject may be enrolled. No other data from the initial screening will be entered into the clinical database for a subject who is re-screened. If performing an echocardiogram (ECHO) or multigated acquisition (MUGA) scan is not possible during screening, an LVEF value from an ECHO/MUGA performed within 60 days before the first dose of study drugs can be used for eligibility determination if no changes in cardiac conditions were observed based on the I, xβzt η-Δβ clinical assessment.

6. STUDY PROCEDURES

A study visit schedule in tabular format is provided in the Schedule of Events tables (Section 17.3). Throughout the treatment period, serum pregnancy tests are to be done as indicated for women of childbearing potential. A pill diary may be dispensed for at-home study drug dosing, as noted in the study procedures and in the Schedule of Events tables.

- The Investigator must not prescribe or administer the study drug until the subject has completed registration. If the Sponsor disqualifies a subject from participation in the clinical study, the Investigator will be notified. The Investigator will then explain this outcome to the relevant subject.

6.2. Randomization

Not applicable.

6.3. Treatment Period

6.3.1. Part 1 (Dose Escalation)

Unless otherwise stated, an activity occurs before study drug administration.

6.3.1.1. Part 1 (Dose Escalation), Cycle 1/Day 1

The following procedures will be completed pre-dose during the Part 1, Cycle 1/Day 1 visit. If the Screening visit for Part 1 is completed within 24 hours of Cycle 1/Day 1, the assessments need not be repeated, with the exception of ECOG Performance Status Scale, vital signs, and 12-lead ECG. Blood samples for safety laboratory tests need not be collected if previously collected within 72 hours of Cycle 1/Day 1.

Perform a complete physical examination and record weight.

Obtain vital sign measurements (systolic and diastolic blood pressure, pulse rate, respiratory rate, and body temperature).

Assess functional status using the ECOG Performance Status Scale.

Obtain blood samples for safety laboratory tests (hematology and serum chemistry).

Obtain a blood sample for PK measurements.

Obtain blood samples for exploratory biomarkers.

Obtain a blood sample for banking plasma.

Obtain a blood sample for serum MIC-1 analysis.

Perform a 12-lead ECG in triplicate after subject has been in supine position for 5 minutes prior.

Record concomitant medications.

Record transfusion (RBC, platelet, other).

Assess subjects for AEs.

Obtain a buccal swab or saliva for pharmacogenomics (PGx).

Informed consent specifically allowing PGx testing sample storage must be obtained before collecting sample.

Administer milademetan per protocol.

Administer quizartinib per protocol.

The following procedures will be completed post-dose during the Part 1, Cycle 1/Day 1 visit:

Obtain vital sign measurements (systolic and diastolic blood pressure, pulse rate, respiratory rate, and body temperature) at 3 hours (\pm 10 minutes) post-dose.

Perform a 12-lead ECG in triplicate at 1, 2, 4, and 6 hours post-dose as indicated in ECG manual. Subject should be in supine position for 5 minutes prior to each reading.

Obtain a blood sample for PK measurements at the following timepoints: 0.5, 1, 2, 3, 4, and 6-8 hours post-dose as indicated in Section 8.

6.3.1.2. Part 1 (Dose Escalation), Cycle 1/Day 2

The following procedures will be performed pre-dose during the Part 1, Cycle 1/Day 2 visit:

Obtain vital sign measurements (systolic and diastolic blood pressure, pulse rate, respiratory rate, and body temperature).

Obtain blood samples for exploratory biomarkers.

Obtain a blood sample for serum MIC-1 analysis.

Obtain a blood sample for PK measurements.

Perform a 12-lead ECG in triplicate after subject has been in supine position for 5 minutes prior.

Record concomitant medications.

Record transfusion (RBC, platelet, other).

Assess subjects for AEs.

Administer milademetan per protocol.

Administer quizartinib per protocol.

Dispense milademetan per protocol (to take home, if regionally required).

Dispense quizartinib per protocol (to take home, if regionally required).

Dispense a pill diary with dose administration instructions (for at-home dosing, if regionally required).

6.3.1.3. Part 1 (Dose Escalation), Cycle 1/Day 8

The following procedures will be performed pre-dose during the Part 1, Cycle 1/Day 8 visit (± 2 days):

- Perform a complete physical examination and record weight.
- Obtain vital sign measurements (systolic and diastolic blood pressure, pulse rate, respiratory rate, and body temperature).
- Assess functional status using the ECOG Performance Status Scale.
- Obtain blood samples for safety laboratory tests (hematology and serum chemistry).
- Obtain blood samples for exploratory biomarkers.
- Obtain a blood sample for serum MIC-1 analysis.
- Obtain a blood sample for PK measurements.
- Obtain a blood sample for banking plasma.
- Perform a 12-lead ECG in triplicate after subject has been in supine position for 5 minutes prior.
- Record concomitant medications.
- Record transfusion (RBC, platelet, other).
- Assess subjects for AEs.
- Administer milademetan per protocol. (Not administered if subject is in the qd 7/28 or qd 3/14 $\times 2$ schedule).
- Administer quizartinib per protocol.
- Dispense milademetan per protocol (to take home, if regionally required). (Not dispensed if subject is in the qd 7/28 or qd 3/14 $\times 2$ schedule).
- Dispense quizartinib per protocol (to take home, if regionally required).
- Dispense and review pill diary (for at-home dosing, if regionally required) and assess treatment compliance.

6.3.1.4. Part 1 (Dose Escalation), Cycle 1/Day 14

The following procedures will be completed pre-dose during the Part 1, Cycle 1/Day 14 visit:

- Perform a complete physical examination and record weight.
- Obtain vital sign measurements (systolic and diastolic blood pressure, pulse rate, respiratory rate, and body temperature).
- Assess functional status using the ECOG Performance Status Scale.
- Obtain blood samples for safety laboratory tests (hematology and serum chemistry).
- Obtain a blood sample for serum MIC-1 analysis.

Obtain a blood sample for PK measurements.

Perform a 12-lead ECG in triplicate after subject has been in supine position for 5 minutes prior.

Record concomitant medications.

Record transfusion (RBC, platelet, other).

Assess subjects for AEs.

Administer milademetan per protocol. (Not administered if subject is in the qd 7/28 or qd 3/14 × 2 schedule).

Administer quizartinib per protocol.

Dispense and review pill diary (for at-home dosing, if regionally required) and assess treatment compliance.

The following procedures will be completed post-dose during the Part 1, Cycle 1/Day 14 visit:

Perform a 12-lead ECG in triplicate at 1, 2, 4, and 6 hours post-dose as indicated in ECG manual. Subject should be in supine position for 5 minutes prior to each reading.

Obtain a blood sample for PK measurements at the following timepoints: 0.5, 1, 2, 3, 4, and 6-8 hours post-dose as indicated in Section 8.

For 60 mg quizartinib cohorts, determine whether the QTcF allows for escalating the quizartinib dose to 60 mg for Day 15 onwards.

6.3.1.5. Part 1 (Dose Escalation), Cycle 1/Day 15

The following procedures will be completed pre-dose during the Part 1, Cycle 1/Day 15 visit:

Perform a 12-lead ECG in triplicate after subject has been in supine position for 5 minutes prior.

Obtain a blood sample for PK measurements.

Record concomitant medications.

Record transfusion (RBC, platelet, other).

Assess subjects for AEs.

Administer quizartinib per protocol.

Administer milademetan per protocol if subject is in the qd 3/14 × 2 dosing schedule.

The following procedures will be completed post-dose during the Part 1, Cycle 1/Day 15 visit:

Perform a 12-lead ECG in triplicate at 3 hours post-dose as indicated in ECG manual. Subject should be in supine position for 5 minutes prior to each reading.

Obtain a blood sample for PK measurements at 3 hours post-dose as indicated in Section 8.

Dispense quizartinib per protocol (to take home, if regionally required).

Dispense milademetan per protocol if subject is in the qd 3/14 × 2 dosing schedule.

6.3.1.6. Part 1 (Dose Escalation), Cycle 1/Day 22

The following procedures will be completed pre-dose during the Part 1, Cycle 1/Day 22 visit (± 2 days):

Perform a 12-lead ECG in triplicate after subject has been in supine position for 5 minutes prior.

Obtain vital sign measurements (systolic and diastolic blood pressure, pulse rate, respiratory rate, and body temperature).

Obtain blood samples for safety laboratory tests (hematology and serum chemistry).

Obtain a blood sample for serum MIC-1 analysis.

Obtain a blood sample for PK measurements.

Record concomitant medications.

Record transfusion (RBC, platelet, other).

Assess subjects for AEs.

Administer quizartinib per protocol.

Dispense quizartinib per protocol (to take home, if regionally required).

Dispense and review pill diary (for at-home dosing, if regionally required) and assess treatment compliance.

The following procedures will be completed post-dose during the Part 1, Cycle 1/Day 22 visit:

Perform a 12-lead ECG in triplicate at 3 hours post-dose as indicated in ECG manual. Subject should be in supine position for 5 minutes prior to each reading.

Obtain a blood sample for PK measurements at 3 hours post-dose as indicated in Section 8.

6.3.1.7. Part 1 (Dose Escalation), Cycle 2/Day 1

The following procedures will be completed pre-dose during the Part 1, Cycle 2/Day 1 visit (± 2 days):

Perform a complete physical examination and record weight.

Obtain vital sign measurements (systolic and diastolic blood pressure, pulse rate, respiratory rate, and body temperature).

Assess functional status using the ECOG Performance Status Scale.

Obtain blood samples for safety laboratory tests (hematology and serum chemistry).

Perform a 12-lead ECG in triplicate after subject has been in supine position for 5 minutes prior.

Obtain a blood sample for PK measurements.

Obtain bone marrow biopsies/aspirates for disease assessment and biomarker tests.

Note: Submission of bone marrow specimens is required for biomarker tests (see details in Section 7.1.1.1 and instructions in the Laboratory Manual).
Additionally, submission of bone marrow samples for MRD analysis is required if <5% blasts in bone marrow is observed.

Obtain blood samples for exploratory biomarkers.

Obtain a blood sample for banking plasma.

Obtain a blood sample for serum MIC-1 analysis.

Record concomitant medications.

Record transfusion (RBC, platelet, other).

Assess subjects for AEs.

Administer milademetan per protocol.

Administer quizartinib per protocol.

Dispense milademetan per protocol (to take home, if regionally required).

Dispense quizartinib per protocol (to take home, if regionally required).

Dispense and review pill diary (for at-home dosing, if regionally required) and assess treatment compliance.

The following procedures will be completed post-dose during the Part 1, Cycle 2/Day 1 visit:

Perform a 12-lead ECG in triplicate at 3 hours post-dose as indicated in ECG manual. Subject should be in supine position for 5 minutes prior to each reading.

Obtain a blood sample for PK measurements at 3 hours post-dose as indicated in Section 8.

6.3.1.8. Part 1 (Dose Escalation), Cycle 2/Day 8

The following procedures will be completed pre-dose during the Part 1, Cycle 2/Day 8 visit (\pm 2 days):

Obtain vital sign measurements (systolic and diastolic blood pressure, pulse rate, respiratory rate, and body temperature).

Obtain blood samples for safety laboratory tests (hematology and serum chemistry).

Perform a 12-lead ECG in triplicate after subject has been in supine position for 5 minutes prior.

Obtain a blood sample for PK measurements.

Record concomitant medications.

Record transfusion (RBC, platelet, other).

Assess subjects for AEs.

Administer milademetan per protocol if subject is in the qd 14/28 dosing schedule.

Administer quizartinib per protocol.

Dispense milademetan per protocol (to take home, if regionally required) if subject is in the qd 14/28 dosing schedule.

Dispense quizartinib per protocol (to take home, if regionally required).

Dispense and review pill diary (for at-home dosing, if regionally required) and assess treatment compliance.

6.3.1.9. Part 1 (Dose Escalation), Cycle 2/Day 15

The following procedures will be completed pre-dose during the Part 1, Cycle 2/Day 15 visit (\pm 2 days):

Perform a complete physical examination and record weight.

Obtain vital sign measurements (systolic and diastolic blood pressure, pulse rate, respiratory rate, and body temperature).

Assess functional status using the ECOG Performance Status Scale.

Obtain blood samples for safety laboratory tests (hematology and serum chemistry).

Perform a 12-lead ECG in triplicate after subject has been in supine position for 5 minutes prior.

Obtain a blood sample for PK measurements.

Record concomitant medications.

Record transfusion (RBC, platelet, other).

Assess subjects for AEs.

Administer quizartinib per protocol.

Administer milademetan per protocol if subject is in the qd 3/14 \times 2 dosing schedule.

Dispense quizartinib per protocol (to take home, if regionally required).

Dispense milademetan per protocol if subject is in the qd 3/14 \times 2 dosing schedule.

Dispense and review pill diary (for at-home dosing, if regionally required) and assess treatment compliance.

6.3.1.10. Part 1 (Dose Escalation), Cycle 2/Day 22

The following procedures will be completed pre-dose during the Part 1, Cycle 2/Day 22 visit (\pm 2 days):

Obtain vital sign measurements (systolic and diastolic blood pressure, pulse rate, respiratory rate, and body temperature).

Obtain blood samples for safety laboratory tests (hematology and serum chemistry).

Perform a 12-lead ECG in triplicate after subject has been in supine position for 5 minutes prior.

Obtain a blood sample for PK measurements.

Record concomitant medications.

Record transfusion (RBC, platelet, other).

Assess subjects for AEs.

Administer quizartinib per protocol.

Dispense quizartinib per protocol (to take home, if regionally required).

Dispense and review pill diary (for at-home dosing, if regionally required) and assess treatment compliance.

6.3.1.11. Part 1 (Dose Escalation), Cycle 3/Day 1

The following procedures will be completed pre-dose during the Part 1, Cycle 3/Day 1 visit (\pm 4 days):

Perform a complete physical examination and record weight.

Obtain vital sign measurements (systolic and diastolic blood pressure, pulse rate, respiratory rate, and body temperature).

Assess functional status using the ECOG Performance Status Scale.

Obtain blood samples for safety laboratory tests (hematology and serum chemistry).

Obtain a serum sample for pregnancy testing in women of childbearing potential.

Perform a 12-lead ECG in triplicate after subject has been in supine position for 5 minutes prior.

Obtain a blood sample for PK measurements.

Obtain bone marrow biopsies/aspirates for disease assessment and biomarker tests.

Note: Submission of bone marrow specimens is required for biomarker tests (see details in Section 7.1.1.1 and instructions in the Laboratory Manual).

Additionally, submission of bone marrow samples for MRD analysis is required if $<5\%$ blasts in bone marrow is observed.

Obtain blood samples for exploratory biomarkers.

Obtain a blood sample for banking plasma.

Record concomitant medications.

Record transfusion (RBC, platelet, other).

Assess subjects for AEs.

Administer milademetan per protocol.

Administer quizartinib per protocol.

Dispense milademetan per protocol (to take home, if regionally required).

Dispense quizartinib per protocol (to take home, if regionally required).

Dispense and review pill diary (for at-home dosing, if regionally required) and assess treatment compliance.

The following procedures will be completed post-dose during the Part 1, Cycle 3/Day 1 visit:

Perform a 12-lead ECG in triplicate at 3 hours post-dose as indicated in ECG manual. Subject should be in supine position for 5 minutes prior to each reading.

Obtain a blood sample for PK measurements at 3 hours post-dose as indicated in Section 8.

6.3.1.12. Part 1 (Dose Escalation), Cycle 3/Days 8, 15, and 22

The following procedures will be completed pre-dose during the Part 1, Cycle 3/Days 8, 15, and 22 visits (± 4 days):

Obtain vital sign measurements (systolic and diastolic blood pressure, pulse rate, respiratory rate, and body temperature).

Obtain blood samples for safety laboratory tests (hematology and serum chemistry).

Perform a 12-lead ECG in triplicate after subject has been in supine position for 5 minutes prior.

Obtain a blood sample for PK measurements.

Record concomitant medications.

Record transfusion (RBC, platelet, other).

Assess subjects for AEs.

Administer milademetan per protocol only on Part 1, Cycle 3/Day 8 visit if subject is in the qd 14/28 dosing schedule and only on Part 1, Cycle 3/Day 15 visit if subject is in qd 3/14 \times 2 dosing schedule (no administration of milademetan for subjects in the qd 7/28 dosing schedule).

Administer quizartinib per protocol.

Dispense milademetan per protocol (to take home, if regionally required) only on Part 1, Cycle 3/Day 8 visit if subject is in the qd 14/28 dosing schedule and only on Part 1, Cycle 3/Day 15 visit if subject is in the qd 3/14 \times 2 dosing schedule (no dispensing of milademetan for subjects in the qd 7/28 dosing schedule).

Dispense quizartinib per protocol (to take home, if regionally required).

Dispense and review pill diary (for at-home dosing, if regionally required) and assess treatment compliance.

6.3.1.13. Part 1 (Dose Escalation), Day 1 of Cycle 4 and All Subsequent Cycles

The following procedures will be performed pre-dose during the Part 1, Cycle 4/Day 1 (± 4 days), and all subsequent cycles on Day 1 (± 4 days):

Perform a complete physical examination and record weight.

Obtain vital sign measurements (systolic and diastolic blood pressure, pulse rate, respiratory rate, and body temperature).

Assess functional status using the ECOG Performance Status Scale.

Obtain blood samples for safety laboratory tests (hematology and serum chemistry). In subjects who develop gastrointestinal (GI) AEs, such as vomiting and diarrhea of SAE, blood chemistry and 12-lead ECGs will be assessed weekly or more frequently as clinically needed until the GI AEs and electrolyte abnormalities are resolved. In subjects with potassium, calcium, and magnesium Grade 1, blood chemistry and 12-lead ECGs will be assessed twice a week.

Obtain a serum sample for pregnancy testing in women of childbearing potential on Day 1 of every 3 cycles from Cycle 3 (ie, Cycles 6, 9, 12, etc).

Perform a 12-lead ECG in triplicate up to Part 1, Cycle 6/Day 1 after subject has been in supine position for 5 minutes prior.

Obtain blood samples for PK measurements up to Part 1, Cycle 6/Day 1.

Obtain bone marrow biopsies/aspirates for disease assessment and biomarker tests (see details in Section 7.1.1 and instructions in the Laboratory Manual):

If subject achieves CR, CRi, or MLFS before Cycle 4/Day 1 (eg, CR on Cycle 3/Day 1), then bone marrow biopsies/aspirates will be not required on Cycle 4/Day 1.

- Perform bone marrow biopsies/aspirates on Day 1 of Cycles 6, 9, and 12 if subject remains in CR, CRi, or MLFS.
- If subject remains in CR, CRi, or MLFS on Cycle 12/Day 1, bone marrow biopsies/aspirates will be required at Day 1 of Cycles 18, 24, and every 6 cycles thereafter.

If subject does not achieve CR, CRi, or MLFS before Cycle 4/Day 1 (eg, PR on Cycle 3/Day 1), then bone marrow biopsies/aspirates will be required on Cycle 4/Day 1 and on Day 1 of every cycle thereafter until subject achieves CR, CRi, or MLFS.

Unscheduled bone marrow biopsies/aspirates can be performed whenever clinically indicated.

Note: Submission of bone marrow specimens beyond Cycle 3/Day 1 is required at the following visits (see details in Section 7.1.1.1 and instructions in the Laboratory Manual):

Bone marrow samples on Day 1 of Cycles 6, 9, 12, 18, 24, and every 6 cycles thereafter.

Bone marrow sample from unscheduled bone marrow biopsies/aspirates when disease progression (relapse or progressive disease) is suspected.

Additionally, submission of bone marrow samples for MRD analysis (eg, flow cytometry and/or next generation sequencing) is required on the day when <5% blasts in bone marrow is observed and/or at the subsequent timepoints for bone marrow sample collection.

Bone marrow samples from other timepoints are not required to be submitted (eg, Cycle 4/Day1).

Obtain blood samples for plasma and exploratory biomarkers analyses (every 3 cycles after Cycle 3).

Obtain a blood sample for banking plasma (every 3 cycles after Cycle 2).

Record concomitant medications.

Record transfusion (RBC, platelet, other).

Assess subjects for AEs.

Administer milademetan per protocol.

Administer quizartinib per protocol.

Dispense milademetan per protocol (to take home, if regionally required).

Dispense quizartinib per protocol (to take home, if regionally required).

Dispense and review pill diary (for at-home dosing, if regionally required) and assess treatment compliance.

The following procedures will be completed post-dose during the Part 1, Cycles 4 to 6 on Day 1:

Perform a 12-lead ECG in triplicate at 3 hours post-dose up to Part 1, Cycle 6/Day 1 as indicated in ECG manual. Subject should be in supine position for 5 minutes prior to each reading.

Obtain blood samples for PK measurements at 3 hours post-dose up to Part 1, Cycle 6/Day 1 as indicated in Section 8.

